3.9. Statistical methods Module 2 Cure rate study

For primary objective 1, we will compare the CIN2/3 cure rates of treatment with cryotherapy (Arm A) or thermal ablation (Arm B) after 12 months of treatment among HIV positive women using Z-test for comparison of proportions in intention-to-treat and per-protocol analyses.

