2.5.1. Cryotherapy

Cryotherapy consists of freezing the lesion and underlying tissue to a temperature of at least -20° Celsius. The treated tissue necrotises and is replaced by new healthy epithelium. A reusable probe is applied to the cervix and the freezing is obtained through decompression of either carbon dioxide (CO2) or nitrous oxide (N2O) gas. The main side-effect is a watery vaginal discharge for up to 2-3 weeks, which is generally well tolerated. The equipment is simple, no electricity is needed and the technique is relatively easy to perform. Cryotherapy can be provided by a variety of healthcare personnel including general doctors, nurses, midwives and auxiliary health workers who can be trained in short sessions. For those reasons, cryotherapy is very suited for LMIC. In addition, it can also be used in a single visit screen-and-treat approach in combination with a screening test that provides immediate results, such as VIA. One potential impediment of the technique is the inadequate availability or elevated cost of the freezing gas. Lesions that are not eligible for cryotherapy are those that reach >2mm in the endocervical canal; are larger than the cryoprobe; cover more than 75% of the ectocervix; and should be treated with LLETZ. Lesions that are suspicious of invasive cancer should be biopsied and treated according to diagnostic work up.

A meta-analysis showed that cryotherapy is 92% and 85% effective to eliminate CIN2 and CIN3, respectively (cure : normal cytology at follow-up) [15].

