2.5.2. Thermal ablation

Thermal ablation is another ablative treatment for CIN, also previously called 'cold coagulation'. The equipment is fairly simple and treatment is based on a 20-40 seconds application (multiple if needed) of a reusable metallic probe that is electrically heated to 100° Celsius, leading to epithelial and stromal destruction of the lesion. The equipment weighs less than 4 kg, which makes it easily portable to field clinics in developing countries. Recently light weight hand held and battery operated models have been developed. Like cryotherapy, thermal ablation can be provided by a variety of healthcare personnel including primary healthcare workers and is typically performed without anaesthesia. The WHO guideline review committee has recently approved recommendations for the use of TA, which will soon be officially published. Similar to cryotherapy, TA is recommended for CIN2/3 lesions, confirmed by histology or not in the context of screen and treat programs.

A previous meta-analysis by Dolman et al. [17] was recently updated by Randall et al. [18]. The update includes 23 reports among 6371 patients treated for histologically confirmed CIN2/3. Lesions were considered as cured if follow-up colposcopy/biopsy was <CIN2 or normal follow-up cytology. Overall cure rate for women treated for CIN2/3 or CIN3 were 94% and 89%, respectively.

The WHO guideline development group concluded that comparing the effects of thermal ablation to cryotherapy indirectly, there is moderate certainty evidence that the benefits and harms of these two treatments were similar. The great majority of these studies were carried out among HIV negative women.

In some studies, especially those from Scotland and UK, used a 2-probe method, in which treatment of the visible glandular epithelium with a small conical probe followed by treatment of the ectocervix with a flat probe. Other studies reported the use of a one-probe method. The WHO expert guideline development group concluded that although application methodology was not always clearly described in the reports,

evidence showed that more women may be cured with a 2-probe method (95%; 95%CI, 93-98%) than a 1-probe method (85%; 95%CI 80-90%).

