3.9.1. Sample size and power calculations

The sample size is based on: 1) the expected difference between the cure rates of cryotherapy and thermal ablation, 2) the lower of the two expected cure rates, and, 3) the prevalence of HSIL+ cases eligible for ablative treatment.

Larger samples sizes will be needed for comparing smaller differences and for comparing cure rates closer to 50%. It is expected that cure rates will be on the range of 70-75% in HIV positive women [28]. Assuming the lowest cure rate to be 70%, 10% difference between cure rates, 20% ineligible for ablative treatment in each arm, 20% attrition after 12 months of treatment, 920 HSIL+ HIV positive cases will be needed in total (387 cases per arm, 146 ineligible) to estimate the 10% difference with 80% power and two-sided type error I of 0.05. For larger differences or the lowest cure rate above 70%, the power to detect the differences will be higher.

Difference* (%)	N total	Attrition (+20%)	Subtotal	Total with 20% ineligibility	n per arm
8	942	236	1178	1472	618
8.5	830	208	1038	1297	545
9	734	184	918	1147	482
9.5	656	164	820	1025	431
10	589	147	736	920	387

Table 6. Number of HSIL+ cases and statistical power for the cure rate objective

Power = 80%. *Starting at 70%

From Module 1, we expect to identify 143 HSIL HPV positive cases (see Table 1). Therefore, we will need to include in this module 777 HSIL cases. Assuming a prevalence of 5% HSIL and a sensitivity of HPV test of 95%, 16,340 HIV positive women should be screened to complete the 920 HSIL cases.

4. Study Methods

For study methods specific for modules 1 and 2 we refer to the sections describing the study outline of the different CESTA modules (3.2.– 3.5; 3.9).

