4.2. Randomisation procedures

The method of randomization will be through the use of pre-printed cards. Each randomisation will have its own set of cards with allocations to one of the screen-and-treat study arms (1: HPV + VIA + treatment or 2: HPV + treatment) and to one of the treatment arms (A: cryotherapy or B: thermal ablation). The Soares big stick design (BSD) [29] algorithm will be used. This algorithm assures the best allocation randomness in a comparison of 14 methods [30]. Using R software, the output of this algorithm is a csv file with the participant number and the arm allocation. The same procedure will be applied on HIV positive and HIV negative women included in the study.

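### The Module 2 primary Z-test is valid but leaves baseline CIN grade and source of randomisation unused; a stratified risk difference would be a small, free gain

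*Protocol*

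**What the plan says.** Protocol section 3.9 gives the primary Module 2 analysis in one sentence. Cure after cryotherapy (arm A) and thermal ablation (arm B) at 12 months is compared "using Z-test for comparison of proportions in intention-to-treat and per-protocol analyses". No covariate or stratum is named.

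Section 3.9.1 sizes the comparison: "Assuming the lowest cure rate to be 70%, 10% difference between cure rates", "with 80% power and two-sided type error I of 0.05", then "20% ineligible for ablative treatment in each arm" and "20% attrition after 12 months of treatment". Table 6 gives 589 evaluable women, 736 after attrition and 920 after ineligibility. The same section deducts 143 cases expected from Module 1 from the 920.

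On prognosis by grade, section 2.5.1 reports that "cryotherapy is 92% and 85% effective to eliminate CIN2 and CIN3, respectively". For thermal ablation, section 2.5.2 reports: "Overall cure rate for women treated for CIN2/3 or CIN3 were 94% and 89%, respectively".

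On randomisation, section 3.8 allocates Module 2 women 1:1 once the biopsy result is known. Section 3.2.1 allocates eligible Module 1 women to sub-arms A and B and states no ratio. Section 4.2 says "Each randomisation will have its own set of cards" and uses a big stick design. It names no stratification by CIN grade, clinic or module.

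**The concern.** Every woman in the primary analysis has a histological grade, CIN2 or CIN3, from a biopsy taken before ablation. Treatment cannot affect that grade, and the protocol's own sources suggest that it predicts cure. Nothing in section 4.2 balances grade between the arms, because the big stick design limits only the overall imbalance. A crude test therefore gives up a little precision and offers no prespecified answer if one arm happens to receive more CIN3.

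The second issue is the source of the women. Module 1 cases count towards the 920, and section 3.2.1 has them randomised to A or B within Module 1. Read with the statement on card sets in section 4.2, this suggests that the primary analysis pools at least two separately randomised groups. If both are allocated 1:1, pooling costs almost nothing. If Module 1 is not 1:1 and cure differs by source, the crude difference carries a bias that a stratified estimate would not. The protocol does not give the Module 1 ratio, so a reader cannot rule this out.

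**Working it through.** **1. The plan's figure.** The pooled two-proportion formula, two-sided 0.05 and 80% power, with 70% against 80%:

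n per arm = [1.96·√(2·0.75·0.25) + 0.8416·√(0.70·0.30 + 0.80·0.20)]² / 0.10² = (1.2003 + 0.5119)² / 0.01 = 293.2, so 294 per arm and 588 in total (stated: 589).

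The other four rows of Table 6 reproduce exactly (942, 830, 734, 656). Inflation also agrees: 589/0.8 = 736 and 736/0.8 = 920. The sample size is thus that of the crude Z-test. All work below uses 589 evaluable women, about 294.5 per arm.

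**2. Inputs that the protocol does not give (assumed).** CIN3 share among CIN2/3: 30% to 70%. CIN2 to CIN3 cure gap: 7 points is the cited cryotherapy contrast (92 − 85); 5 to 20 points is the range tried.

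**3. Gain from stratifying by grade.** With CIN3 share f and gap g equal in both arms, stratification removes f(1−f)g² from each arm's variance.

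- Crude: 0.70·0.30 + 0.80·0.20 = 0.37. SE = √(0.37/294.5) = 3.54 points. Power = Φ(0.10/0.03544 − 1.96) = 80.6% (unpooled SE; 80.2% with the pooled formula).
- Stratified, f = 0.5, g = 0.07: 0.37 − 2·0.25·0.0049 = 0.36755. Relative efficiency = 0.37/0.36755 = 1.007.

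**4. Chance imbalance.** The SD of the between-arm difference in CIN3 share is √(2·0.25/294.5) = 4.1 points at f = 0.5 (3.8 at 30% or 70%). Multiplying by g gives the shift in the crude cure difference.

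| Gap g (f = 0.5) | Relative efficiency | Equivalent N | Power, stratified | Shift, 1 SD | Shift, 1.96 SD |
|---|---|---|---|---|---|
| 5 points | 1.003 | 587 | 80.7% | 0.21 | 0.40 |
| 7 points (cited) | 1.007 | 585 | 80.8% | 0.29 | 0.57 |
| 10 points | 1.014 | 581 | 81.1% | 0.41 | 0.81 |
| 15 points | 1.031 | 571 | 81.7% | 0.62 | 1.21 |
| 20 points | 1.057 | 557 | 82.7% | 0.82 | 1.62 |

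Shifts are in percentage points, against an SE of 3.54. At a 7-point gap the power gain over f = 30% to 70% is 0.2 to 0.3 point.

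**5. Simulation.** 40,000 trials of 589 women, half CIN3, Module 1 share 143/920 = 15.5%, both sources allocated 1:1. The Z-test was compared with a Cochran-Mantel-Haenszel test stratified by grade and source.

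- No cure difference between sources: power 80.4% against 80.5% (7-point gap), 80.5% against 81.6% (15) and 80.2% against 82.3% (20).
- An assumed 10-point cure difference between sources added at most about 0.3 to 0.4 point to the gain.
- Type I error of both tests lay between 4.8% and 5.2%.

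**6. Source of randomisation.** The bias in the crude difference equals (Module 1 share in arm B − Module 1 share in arm A) × (cure difference between sources). It is zero under 1:1 allocation in both sources. It cannot be sized otherwise, because the protocol gives neither the Module 1 ratio nor cure by source.

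**7. Are the strata large enough?** Evaluable Module 1 women: 589·143/920 ≈ 92. With half CIN3 and equal allocation, that is about 23 per arm in each of the two smaller strata.

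**The case against.** The strongest reply is that nothing is wrong. The Z-test holds its level and agrees with Table 6. Chance imbalance in grade does not bias a randomised comparison, and its variability is already in the crude standard error. All of this stands. A reader might infer that ignoring CIN grade makes the primary test invalid or biased; the calculations do not support that.

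A reader might also infer that the analysis must be stratified to match the randomisation. For CIN grade the protocol does not support this, since section 4.2 names no grade stratum. For source, section 3.8 says only that Module 1 cases can be invited into Module 2, and no passage states which cards they use. Separate card sets are a reasonable reading of sections 3.2.1, 3.8, 3.9.1 and 4.2 together, but still an inference. Nor would stratifying by source separate treatment at the screening visit from treatment after histology. Section 3.2.1 also randomises Arm 1 women left untreated after screening once their biopsy shows CIN2+, so Module 1 contains both pathways.

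The prognostic evidence is thin. The 92% and 85% define cure by normal cytology and are not given as HIV-positive rates. The thermal ablation pair sets CIN2/3 combined against CIN3, so it is not a CIN2 to CIN3 contrast, and most of those studies were in HIV-negative women. Section 2.7 calls CIN2 poorly reproducible, which would tend to weaken a grade stratum. These points stand and keep the expected gain small.

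Finally, adjustment is often left to the SAP. That would answer a complaint of silence. Here the protocol states a primary test, and the suggestion is to improve that stated choice. A sponsor could reasonably prefer to add the stratified estimate as a supplementary analysis.

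**Conclusion.** The point holds as an optional improvement. The primary test is valid but crude, and it leaves unused a baseline grade that every analysed woman has.

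The benefit is about 0.2 to 0.3 power point (about 4 of 589 women) at the only CIN2 to CIN3 gap cited. It reaches about 2 points only at an assumed 20-point gap. A 7-point excess of CIN3 in one arm would be about 1.7 SD (7/4.1). With an assumed 15-point gap it would move the cure difference by about 1 point (7 × 0.15), under a third of the standard error.

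Stratifying by source adds almost nothing if Module 1 is allocated 1:1, and removes a possible bias if it is not. These results rest on an assumed CIN3 share, on assumed gaps beyond 7 points, and on the inference that Module 1 women are randomised on their own cards.

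**What to change.** In section 3.9, make the primary analysis a Mantel-Haenszel test and risk difference with 95% confidence interval, stratified by baseline CIN grade (CIN2, CIN3) and by source of randomisation (Module 1 or Module 2 cards). Keep the crude Z-test as a check. State the Module 1 A:B ratio and which cards Module 1 women use, so that the source stratum is defined.

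The estimate stays on the risk-difference scale. With near-equal allocation within strata, the Mantel-Haenszel weights are close to stratum size, so the target is close to the crude difference. The sample size can stay as it is. The cost is a sentence or two of wording, with no extra data and no extra women. The change should be made before outcome data are seen.

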3.9.1. Sample size and power calculations

The sample size is based on: 1) the expected difference between the cure rates of cryotherapy and thermal ablation, 2) the lower of the two expected cure rates, and, 3) the prevalence of HSIL+ cases eligible for ablative treatment.

Larger samples sizes will be needed for comparing smaller differences and for comparing cure rates closer to 50%. It is expected that cure rates will be on the range of 70-75% in HIV positive women [28]. Assuming the lowest cure rate to be 70%, 10% difference between cure rates, 20% ineligible for ablative treatment in each arm, 20% attrition after 12 months of treatment, 920 HSIL+ HIV positive cases will be needed in total (387 cases per arm, 146 ineligible) to estimate the 10% difference with 80% power and two-sided type error I of 0.05. For larger differences or the lowest cure rate above 70%, the power to detect the differences will be higher.

Difference* (%)	N total	Attrition (+20%)	Subtotal	Total with 20% ineligibility	n per arm
8	942	236	1178	1472	618
8.5	830	208	1038	1297	545
9	734	184	918	1147	482
9.5	656	164	820	1025	431
10	589	147	736	920	387

Table 6. Number of HSIL+ cases and statistical power for the cure rate objective

Power = 80%. *Starting at 70%

From Module 1, we expect to identify 143 HSIL HPV positive cases (see Table 1). Therefore, we will need to include in this module 777 HSIL cases. Assuming a prevalence of 5% HSIL and a sensitivity of HPV test of 95%, 16,340 HIV positive women should be screened to complete the 920 HSIL cases.

4. Study Methods

For study methods specific for modules 1 and 2 we refer to the sections describing the study outline of the different CESTA modules (3.2.– 3.5; 3.9).

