Novel "patient navigation" tools are being developed and implemented within the SEVIA platform. Patient navigation, first implemented in 1990, is a barrier-focused intervention that targets a defined set of health services required to complete a process of cancer-related care [20]. The provision of patient navigation services has been shown to reduce delays in patients accessing the continuum of cancer care services, with an emphasis on timeliness of diagnosis and treatment and a reduction in the number of patients lost to follow-up in high-income countries. The patient navigation tools for CESTA will be informed by the literature (scoping review in progress), and previous experience with mHealth navigation for breast cancer early diagnosis by community health workers in rural Bangladesh [21]. In our study, we will assess the difference in performance of VIA and VAT as well as attrition rates in clinics that use SEVIA, compared to clinics that do not.

2.7. The use of cervical intraepithelial neoplasia (CIN) and Lower Anogenital Squamous Terminology Standardization (LAST) terminology for cervical histology

Histology will is classified using the cervical intraepithelial neoplasia (CIN) classification. CIN1 corresponds to HPV infection, CIN3 is a highly reproducible cancer precursor and CIN2 is an intermediate and poorly reproducible category and represents a mixture of HPV infections (CIN 1) and true cancer precursors (CIN3). Despite the uncertainty associated with CIN2, it is recommended as the cut-off for treatment, that is, women with CIN2 or worse lesions (CIN2+) should receive adequate treatment [4]. The use of histological high-grade intraepithelial lesion (HSIL) has recently been proposed under the Lower Anogenital Squamous Terminology Standardization (LAST) project [22]. LAST incorporates the current knowledge of HPV biology and the use of biomarkers to improve diagnosis, such as *p*16 immunohistochemistry (IHC) particularly for evaluating whether a diagnosis of CIN2 represents true high-grade cervical disease. Histological HSIL includes CIN2 *p*16 positive, CIN3 and adenocarcinoma in situ (AIS), better reflecting precancer lesions. Therefore, the gold standard for final outcome analysis of this study will be histological HSIL to compare the performance of HPV testing with VIA triage followed by treatment with that of HPV followed by treatment, but we will use CIN2 as a cut-off for treatment as currently recommended.

3. Modules of the CESTA study

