3.6. Ancillary studies

We will obtain aliquots from HPV samples from participants in the study that will be stored at -80C. These samples can later be used to evaluate the performance of novel screening and triage methods for cervical cancer (HPV genotyping, oncoprotein tests, automated visual evaluation (AVE), and others).

3.7. CESTA Module 2: Randomized controlled trial to compare the cure rate of CIN2+ in HIV positive women treated by thermal ablation and cryotherapy (see figure 4)

3.7.1. Primary Objectives:

To compare the CIN2/3 cure rates of treatment with cryotherapy and thermal ablation
12 months after the treatment in HIV positive women.

2. To model the cost-effectiveness of treatment of CIN2/3 by cryotherapy *vs.* thermal ablation in HIV positive populations.

3.7.2. Secondary Objectives:

- 1. To compare the CIN2/3 cure rates of cryotherapy and TA 24 months after the treatment in HIV positive women.
- 2. To compare the histological HSIL cure rate of cryotherapy and TA after 12 and 24 months.
- 3. To assess patient adherence to study visits in clinics using SEVIA or not.
- 4. To assess the performance of VIA as a test of cure 1 year after treatment.
- 5. To estimate the HPV infection clearance rate after one year of the treatment.
- 6. To describe the safety and side effects of cryotherapy and thermal ablation.
- 7. To assess and compare the HIV shedding among women treated with cryotherapy and thermal ablation.

3.8. Study outline CESTA Module 2

The CESTA Module 2 is a randomised controlled trial to compare the cure rate of cryotherapy to thermal ablation HIV positive women. Women with diagnosed cytological LSIL+ (LSIL; HSIL; or ASC-H) at one of the estimated 8-9 involved ARV clinics in South Africa, all situated preferably around Durban, will be invited to one of the CESTA clinics. A total of 920 HIV positive women with CIN2/3 will need to be included in this module to obtain sufficient study power (see section 3.10.1). Some estimated 143 women will already be detected with CIN2/3 in the CESTA Module 1 and can therefore be invited to participate in the CESTA Module 2. This mean that we estimate that CESTA module 2 will need to identify another 777 women with CIN2/3.

Since 2018, women are routinely screened at ARV clinics with liquid based cytology every 3 years in South Africa. We will access the results of those women already screened at the clinics with permission of the clinics administration and the women themselves.

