Women with LSIL+ will attend the closest CESTA study clinic. After informed giving written informed consent, the nurse will take some short questionnaires on demographics and sexual history, and socio-economic characteristics. A health economics questionnaire focused on

participant travel time and expenditures will also be administered. The nurse will collect 2-4 biopsies, with the same procedure as described under Module 1 (section 3.2.1.). Women will then receive an appointment for an additional biopsy results visit. At that visit, all women with CIN2 or 3 without glandular lesions and eligible for ablative treatment through VAT will be randomized in a 1:1 ratio into cryotherapy and thermal ablation, performed by the nurse at the same visit after taking 2-3 pictures with the SEVIA application. Ablation ineligible women will be referred to colposcopy and will be managed and treated appropriately including LLETZ. Women with normal or CIN1 biopsy results will be exited from the study and referred back to the ARV clinic to follow the South Africa standard care recommendations, i.e. rescreening after 1 year.

The VAT examination is inadequate if the SCJ is not completely seen and in that case, the nurse will obtain an endocervical brush for cytology and the women will be sent to the colposcopist when the cytology results are available.

Similarly as in Module 1 (section 3.2.1), women who receive treatment will be called by telephone 1 and 4 weeks after treatment and answer a questionnaire on perceived side-effects and acceptability of treatment. The nurse will take the necessary actions if serious side-effects are reported.

In addition, all treated women will be recalled at 12 and 24 months for a follow-up visit including HPV testing, VIA, colposcopy and biopsy on all HPV positive women, and those with CIN2+ will be treated as appropriate. The SEVIA application will also be used for quality control of the VAT by the nurse, and for patient navigation, as described in Module 1.

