4.3. Duration of subject participation

For all women, the study will include one round of HPV testing. HPV negative women will finish their participation in the study after this first round.

In Module 1, all HPV positive women with or without VIA triage will have a follow-up HPV test at 12 months, and will end their participation if the HPV test at 12 months is negative or after <CIN2 histology on biopsy collected at the colposcopy visit or after treatment (LLETZ or other) for CIN2+.

In Module 2, women with CIN2/3 on biopsy will be randomized into TA or cryotherapy. Women that are ineligible for ablative treatment will be referred to colposcopy for appropriate management and all other women with LSIL+ cytology will be exited from the study and referred back to the ARV clinic for follow up according to South African standard of care. All treated women will attend a FU visit at 12 mo. and 24 mo. with HPV testing, VIA, and colposcopy-directed biopsies on HPV positive women to detect remaining/recurrent disease. At the time of exit, all women will be given clear indications on how to continue with regular screening or with any needed follow-up under the local health system.

5. Ethical considerations

The study will be approved by the IARC and local ethical committees of participating countries: currently being the Biomedical Research Ethics committee (BREC) at the University of KwaZulu-Natal and the "Comité National d'Ethique pour la Recherche en Santé" under the Ministère de la Santé et de l'Action Sociale, Dakar. All women in the study will sign informed consent forms approved by IARC's and the local ethical committees.

The informed consent form will include details on the background, procedures of the study, risks and benefits, statement of confidentiality, specimen use and study staff to contact (informed consent document in annex).

The study is considered minimal risk and the procedures are standard practice in cervical cancer screening programs. The clinical procedures to be performed were developed by a team of clinicians including colposcopists mainly considering the safety of the participants in terms of reduction of cervical cancer risk, and all the procedures are consistent with standard medical practice and/or WHO recommendations, including thermal ablation.

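### Section 3.9.1 sizes Module 2 screening (16,340 women) on HPV-test sensitivity, although section 3.8 finds the cases through LSIL+ cytology and biopsy

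*Protocol*

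**What the plan says.** Section 3.9.1 of the protocol sets the Module 2 requirement at 920 cases, expects 143 of them from Module 1, and leaves 777 to be found. It then assumes 5% HSIL prevalence and "a sensitivity of HPV test of 95%, 16,340 HIV positive women should be screened to complete the 920 HSIL cases".

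The executive summary and section 3.8 describe how the 777 are found. The study looks at routine three-yearly liquid based cytology results from an estimated 8-9 ARV clinics and invites women whose result is LSIL or worse: "Women with LSIL+ will attend the closest CESTA study clinic". There they consent and have biopsies. At a later results visit, "all women with CIN2 or 3 without glandular lesions and eligible for ablative treatment through VAT will be randomized". Section 3.8 mentions no HPV test before randomisation; HPV testing appears there only at the 12- and 24-month visits.

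Section 4.3 opens more broadly: "For all women, the study will include one round of HPV testing", and "HPV negative women will finish their participation in the study after this first round". Its own Module 2 paragraph nevertheless follows section 3.8. Women with CIN2/3 on biopsy are randomised, those not eligible for ablation go to colposcopy, and "all other women with LSIL+ cytology will be exited from the study".

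**The concern.** The number of women who must be screened to yield a fixed number of cases depends on the test that leads them to biopsy. In Module 2 that test is cytology. A woman who has CIN2/3 but no LSIL+ result is never invited, and a woman with LSIL+ who does not attend for biopsy is never diagnosed. Neither loss enters the calculation, which uses the sensitivity of a different test.

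The 95% cannot be defended as belonging to the Module 1 contribution, because the 143 cases found by HPV testing are subtracted before the division.

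At stake is the only stated figure for the screened population needed to supply Module 2. It bears on whether 8-9 clinics are enough and how long recruitment would take.

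**Working it through.** **Inputs, all from section 3.9.1:** 920 cases in total; 143 from Module 1; 5% HSIL prevalence; 95% HPV-test sensitivity; 16,340 women to be screened.

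**1. Reproduce the protocol's figure.**
- Remaining cases: 920 − 143 = 777.
- Number to screen = cases / (prevalence × sensitivity) = 777 / (0.05 × 0.95) = 16,358.
- With intermediate truncation: 777 / 0.95 = 817.9, taken as 817; 817 / 0.05 = 16,340.

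The stated figure is reproduced exactly with the truncation and to within 0.1% without it. The 95% in it is therefore the HPV-test sensitivity. The same formula gives the Module 1 yield, 3,000 × 0.05 × 0.95 = 142.5, or 143. It suits Module 1, where HPV testing is the entry test.

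**2. Formula that matches the section 3.8 pathway.**
- Number to screen = 777 / (prevalence × capture).
- Capture = (probability that a woman with CIN2/3 has an LSIL+ result) × (probability that she then attends for biopsy).

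**3. Break-even from the protocol's own figures.**
- 777 / 16,340 = 0.0476.
- 0.0476 / 0.05 = 0.951.

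At 5% prevalence, cytology sensitivity and biopsy attendance together must reach about 95% for 16,340 to hold. The protocol gives a value for neither. Section 2.1 describes cytology's sensitivity as limited, while section 2.3 puts HPV testing typically above 90%.

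**4. Illustrative range.** The capture values are assumptions; prevalence stays at the protocol's 5%.

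| Assumed capture | 777 / (0.05 × capture) | Ratio to 16,340 |
|---|---|---|
| 90% | 17,267 | 1.06 |
| 80% | 19,425 | 1.19 |
| 70% | 22,200 | 1.36 |
| 60% | 25,900 | 1.59 |

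**5. What does not move.** The 920 follows from the cure rates, attrition and ineligibility. In Table 6, 589 becomes 736 after attrition, and 736 / 0.8 = 920. No screening sensitivity enters that chain, so 920, 387 per arm and 80% power are unaffected by this point.

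**The case against.** **Nothing in the trial's inference uses 16,340.** It appears once, at the end of section 3.9.1, and is not a cap. The operational target is 777 women with CIN2/3, and the study reads cytology results that already exist instead of doing the screening itself. This stands, and it limits the point to planning. A reader might infer that Module 2 is underpowered. The documents do not support that: the number of cases to be randomised is set without reference to how they are found.

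**The arithmetic is right.** This also stands. The fault is an input that conflicts with the design, not a miscalculation.

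**Section 4.3 gives every woman an HPV test.** Its opening sentence can be read that way, but its Module 2 paragraph and section 3.8 place HPV testing at follow-up only, and the specific text is the more natural guide. Even if an entry HPV test did apply, it would come on top of cytology, so the cytology term would still be missing. Multiplying the two sensitivities would then assume that the tests miss lesions independently. Nothing in the protocol supports that assumption, so no such figure is given here.

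**The 5% prevalence may be wrong as well.** A reader might infer this from section 2.7, where "Histological HSIL includes CIN2 *p*16 positive, CIN3 and adenocarcinoma in situ (AIS), better reflecting precancer lesions", set against CIN2/3 without glandular lesions as the randomisation criterion. That inference is speculative. For planning, the protocol uses HSIL and CIN2/3 for the same 143, 777 and 920 cases. The differences also pull in opposite directions: including p16-negative CIN2 would raise the count, and excluding AIS would lower it. No figure in the document shows a material gap.

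**Conclusion.** The point holds as an internal inconsistency with an effect on feasibility only. Section 3.9.1 derives 16,340 from a test that does not select Module 2 women, and it omits cytology capture and biopsy attendance, which do determine the yield.

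At the protocol's 5% prevalence, any combined capture below about 95% puts the requirement above 16,340. Capture of 90% to 60% would mean about 17,270 to 25,900 women, or 6% to 59% more. Spread evenly over 8-9 clinics, 16,340 is about 1,820 to 2,040 women per clinic, and 25,900 is about 2,880 to 3,240. These ranges rest on the assumed capture values and on 5% prevalence.

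A reader might conclude that the protocol proves a specific shortfall. It does not: without a cytology sensitivity, an LSIL+ rate or an attendance rate, no single corrected number can be calculated. What the protocol does show is that its figure requires about 95% capture and that nothing in the document justifies this. The correction is worth making but of low priority.

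**What to change.** In section 3.9.1, replace the HPV-test sensitivity with a sourced sensitivity of LSIL+ cytology for CIN2/3 in HIV positive women, or size directly from the expected CIN2/3 yield among LSIL+ women. Add an allowance for attendance at biopsy, and restate 16,340 as the resulting figure or range.

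As a minor point, limit the general sentence in section 4.3 on one round of HPV testing to Module 1, or state whether Module 2 women have an HPV test at entry.

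The text change is small, but the inputs are not in the protocol, so a cytology yield and an attendance rate must be sourced. The planning figure will be wider and probably less favourable. No additional women need be randomised, and the 920 cases, 387 per arm and 80% power stay as they are.
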